#### 8.4.8. Prone Positioning

During the period of mechanical ventilation, it will be documented whether or not at least 12 hours of prone positioning was conducted on each day. Descriptive summaries of the percent of days in prone position for at least 12 hours during intubation will be presented in a table.

## 9. SUMMARY OF INTERIM AND DMC ANALYSES

### 9.1.1.1. Interim Analysis

The originally planned Interim Analysis will not be performed due to Sponsor decision to stop the study early.

### 9.1.1.2. Data Monitoring Committee Analysis

An independent DMC will monitor the clinical data for safety and efficacy and will meet at least monthly throughout the duration of the study. The DMC will provide recommendations for continuing or stopping the study for safety or futility in accordance with the DMC charter. Stopping criteria are prespecified in study protocol Section 7.4.2 and Section 13.8.1.1.

In order to perform their monitoring function, the DMC will have access to unblinded safety to ensure the safety of the participants in the study. Efficacy data will be delivered to the DMC as needed to perform their functions. The DMC will also review the results of the planned interim analysis.

Only descriptive analysis will be performed (ie, no statistical hypothesis testing will be performed). All analyses will be performed by a designated clinical research organization independent of Sage.

Sage team will remain blinded for all the DMC and interim analysis data until the end of study.

Please refer to the DMC Charter for additional details.

## **11. LIST OF APPENDICES**

## APPENDIX A. HANDLING OF MISSING DATES

Dates missing the day or both the day and month of the year will adhere to the following conventions in order to classify TEAEs and to classify prior and concomitant medications.

In general, listings will present the actual partial or missing values rather than the imputed values that may be used in derivation. In instances where imputed values will be presented, imputed values will be flagged.

### Adverse Events

If the AE start date is completely missing, do not impute a date but consider it as TEAE, unless the AE end date is before the initiation of treatment, in which case the AE will be considered prior.

For partial AE start dates:

- When the year is known, but the month and day is unknown, then:
  - If the year matches the year of initiation of study drug and the end date (if present) is after the initiation of study drug, or AE is ongoing, then impute as the month and day of the initiation of the study drug date + 1 day.
  - If the year of AE onset < year of initiation of the treatment, then the month and day will be set to December 31st.
  - If the year of AE onset > the year of initiation of treatment, then the month and day will be set to January 1st.
- If the year and month are known, but the day is unknown, then:
  - If the year of AE onset = the year of initiation of the treatment and:
    - the month of AE onset = the month of initiation of the treatment, then the day will be set to the day of initiation of the treatment.
    - the month of AE onset < the month of initiation of the treatment, then the day will be set to the last day of month.
    - if the month of AE onset > the month of initiation of the treatment, then the day will be set to the 1st day of month.
  - If the year of AE onset < the year of initiation of the treatment, then the day will be set to the last day of month.
  - If the year of AE onset > the year of initiation of the treatment, then the day will be set to the 1st day of month.

If the imputed AE onset date is after the AE stop date, then the onset date will be set to the stop date.

- When the year and day are present and the month is missing, treat it as if the day is missing, and only year is present. Follow the imputation rules for “year is known, but the month and day is unknown”.
- When the year is missing, but the month and/or day is known, treat this date as missing; do not impute.

**Dates in Disease History (Dates of diagnosis, current episode, first episode)**

- If the year is present and the month and day are missing, then the month and day will be set to January 1.
- If the year and day are present and the month is missing, then the month will be set to January.
- If the year and month are present and the day is missing, then the day will be set to the 1st day of month

**Prior and Concomitant Medications**

For the partial start date of medication:

- If the year is present and the month and day are missing, then the month and day will be set to January 1.
- If the year and day are present and the month is missing, then the month will be set to January.
- If the year and month are present and the day is missing, then the day will be set to the 1st day of month.
- If the imputed start date of medication is after the non-imputed end date of medication, then the start date will be set to the end date of medication.

For the partial end date of medication:

- If the year is present and the month and day are missing, then the month and day will be set to December 31.
- If the year and day are present and the month is missing, then the month will be set to December. If the year and month are present and the day is missing, then the day will be set to the last day of the month.
- If the year and day are present and the month is missing, then treat it as if the day is also missing. Set the month and day to be December 31.

Statistical Analysis Plan Methods Version 1.0 19 November 2021  
Protocol Number: 547-ARD-301 (Version 5.0 24 February 2021)

[figure not shown]
Sage Therapeutics, Inc.  
CONFIDENTIAL

## APPENDIX B. LIST OF DISPLAYS

[figure not shown]
Statistical Analysis Plan Methods Version 1.0 19 November 2021  
Protocol Number: 547-ARD-301 (Version 5.0 24 February 2021)

Sage Therapeutics, Inc.  
CONFIDENTIAL

Statistical Analysis Plan Methods Version 1.0 19 November 2021  
Protocol Number: 547-ARD-301 (Version 5.0 24 February 2021)

Sage Therapeutics, Inc.  
CONFIDENTIAL

**APPENDIX D. PROCEDURAL TERMS USED IN THE IDENTIFICATION OF RESPIRATORY FAILURE AND UNSUCCESSFUL EXTUBATION**

Verbatim Procedural Term †	Interpretation Relative to Respiratory Failure	Interpretation Relative to Extubation
1. Bronchoscopy	No impact on determination of respiratory failure	No impact on determination of unsuccessful extubation
2. Chest Tube Insertion	No impact on determination of respiratory failure	No impact on determination of unsuccessful extubation
3. CPR	No impact on determination of respiratory failure	No impact on determination of unsuccessful extubation
4. ECMO	Respiratory failure	Extubation considered unsuccessful if within 48 hours of extubation
5. Initiation of Non-Invasive Positive Pressure Ventilation	Respiratory failure	Extubation considered unsuccessful if within 48 hours of extubation
6. Initiation of Oxygen Delivery by High-Flow Nasal Cannula	Respiratory failure	No impact on determination of unsuccessful extubation
7. Intubation	Respiratory failure	Extubation considered unsuccessful if within 48 hours of extubation

8. Intubation/ Brochoscopy/ Cauterization	Respiratory failure	Extubation considered unsuccessful if within 48 hours of extubation
9. Mechanical Ventilation	Respiratory failure	Extubation considered unsuccessful if within 48 hours of extubation
10. None: Extubated to 4L NC	Respiratory failure	No impact on determination of unsuccessful extubation
11. Pneumothorax, Right	No impact on determination of respiratory failure	No impact on determination of unsuccessful extubation
12. PS/CPAP	Respiratory failure	Extubation considered unsuccessful if within 48 hours of extubation
13. Reintubation	Respiratory failure	Extubation considered unsuccessful if within 48 hours of extubation
14. Tracheostomy	No impact on determination of respiratory failure	No impact on determination of unsuccessful extubation

†Mis-spellings present in the clinical database are displayed as-is in this table

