**11.1.7. Data Collection at Follow-Up**

As applicable, the following will be documented during the follow-up visit(s):

- Dates and times of extubation and discontinuation of mechanical ventilation
  - The duration of time on mechanical ventilation will be calculated
- Dates and times of reintubation and re-initiation of mechanical ventilation
- Whether or not the participant requires oxygen delivered by high-flow nasal cannula (heated, humidified oxygen delivered via reinforced nasal cannula at flow rates >20L/min with fraction of delivered oxygen  $\geq 0.5$ ), and if so the date and time of initiation of oxygen delivery by high-flow nasal cannula
- Whether or not the participant requires noninvasive positive pressure ventilation and if so, the date and time of initiation of noninvasive positive pressure ventilation
- Whether or not the participant progressed to ECMO, and if so, the date and time of initiation and (as applicable) completion of ECMO
- Whether or not the participant progressed to tracheostomy, and if so, the date and time of the tracheostomy procedure
- Whether or not the participant died, and if so, the date, time, and cause of death

[REDACTED]

[REDACTED]

[REDACTED]

[REDACTED]

[REDACTED]

[REDACTED]

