### 8.3.1. Definition of Efficacy Endpoints

### 8.3.1.1. Proportion of participants alive and free of respiratory failure at Day 28

The primary efficacy endpoint is the proportion of participants alive and free of respiratory failure at Day 28. Respiratory failure is defined based on resource utilization, requiring at least one of the following:

- Endotracheal intubation and mechanical ventilation
- Oxygen delivered by high-flow nasal cannula (heated, humidified oxygen delivered via reinforced nasal cannula at flow rates >20 L/min with fraction of delivered oxygen  $\geq 0.5$ )
- Noninvasive positive pressure ventilation
- Extracorporeal membrane oxygenation (ECMO)

Please see Appendix D for a detailed breakdown of the Procedural terms used to identify subjects with respiratory failure.

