### 8.3.2. Analysis of Primary Efficacy Endpoint

The primary efficacy endpoint is the proportion of participants alive and free of respiratory failure at Visit 11 (Day 28  $\pm$  3 days).

- If a participant dies prior to Visit 11, the participant will be assigned a value of “no” for the primary endpoint.
- Participants discontinuing the study for reasons other than death and prior to Visit 11 will not be included in the primary analysis.

The difference in the proportions between brexanolone and placebo will be analyzed using the SAS procedure GENMOD. In this model, the proportion will be the response variable, and the predictor variables will be treatment arm and age group (<70 or  $\geq$ 70 years).

Participants will be analyzed according to their actual age group, regardless of the age group used for randomization purposes. The proportion will be directly modeled using the binomial distribution with identity link. The point estimate, confidence interval, and p-value for the difference in the fitted proportions will be obtained using the “LSMEANS” statement to

 Lack of endotracheal intubation, for purposes of the Primary Efficacy Endpoint, does not require a subsequent  $>48$  hour period of time without need for reintubation or noninvasive ventilation.

produce estimated treatment differences (ie, differences in proportions). A sample SAS code is as follows:

```
proc genmod data=indata;
  class trt01p agegr1;
  model aval = trt01p agegr1 / dist=binomial link=identity;
  lsmeans trt01p / diff cl;
run;
```

Please see Appendix D for a detailed breakdown of the Procedural terms used to identify subjects with lack of respiratory failure.

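### SAP Appendix D row 10 codes extubation to 4 L nasal cannula as respiratory failure, which contradicts the primary endpoint definition and could turn a responder into a non-responder

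*SAP*

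**What the plan says.** SAP 8.3.1.1 sets the rule for the primary endpoint: "Respiratory failure is defined based on resource utilization, requiring at least one of the following". Four supports follow:

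1. "Endotracheal intubation and mechanical ventilation"
2. high-flow nasal cannula
3. noninvasive positive pressure ventilation
4. ECMO

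The high-flow item has a numerical threshold: oxygen "delivered via reinforced nasal cannula at flow rates >20 L/min with fraction of delivered oxygen" of at least 0.5. Protocol 11.1.7 uses the same threshold for data collection at follow-up: "heated, humidified oxygen delivered via reinforced nasal cannula at flow rates >20L/min with fraction of delivered oxygen" of at least 0.5.

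SAP 8.3.1.1 refers to Appendix D for the terms that identify respiratory failure. SAP 8.3.2 does the same for its absence: "Please see Appendix D for a detailed breakdown of the Procedural terms used to identify subjects with lack of respiratory failure".

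Appendix D lists 14 recorded procedure terms, each with one code for respiratory failure and one for unsuccessful extubation. Row 6 is "Initiation of Oxygen Delivery by High-Flow Nasal Cannula", coded as respiratory failure with no impact on extubation. Row 10 is "None: Extubated to 4L NC", coded the same way. The table's only footnote concerns spelling: "Mis-spellings present in the clinical database are displayed as-is in this table".

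**The concern.** The definition and the table that puts it into effect disagree. Someone extubated to 4 L by nasal cannula is off the ventilator and on low-flow oxygen, which the definition does not count as respiratory failure. The table says it is.

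The row does not look hypothetical. The terms are presented as verbatim, and the footnote says that they are shown as they stand in the clinical database, so at least one such record appears to exist. A programmer who follows Appendix D would then code that record against the stated endpoint.

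What is at stake is a responder counted as a non-responder on the primary endpoint, in a study stopped early, where each participant may weigh more than planned. A correction made after unblinding would also be open to the charge that it was driven by the result.

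**Working it through.** **Step 1. The plan's own figure.** SAP 5.2 gives about 100 participants, 50% against 77%, a chi-square test, two-sided alpha 0.05 and 80% power. SAP 5.3 gives 1:1 allocation.

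- Mean proportion = (0.50 + 0.77)/2 = 0.635, so the pooled term is 2 × 0.635 × 0.365 = 0.4636.
- The unpooled term is 0.50 × 0.50 + 0.77 × 0.23 = 0.4271.
- n per arm = [1.960 × √0.4636 + 0.842 × √0.4271]² / 0.27² = 48.7, rounded up to 49.
- Power at 50 per arm = Φ[(0.27 − 1.960 × √(0.4636/50)) / √(0.4271/50)] = Φ(0.879) = 81.0%.

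The stated 80% is reproduced. It does not depend on row 10 and does not change if the row is recoded.

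**Step 2. Row 10 against each criterion in SAP 8.3.1.1.**

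| Criterion | What row 10 records | Met? |
|---|---|---|
| Intubation and mechanical ventilation | Extubated | No |
| High-flow cannula, >20 L/min and oxygen fraction ≥0.5 | 4 L by cannula; 4/20 = 0.2 of the flow to be exceeded | No |
| Noninvasive positive pressure ventilation | Not recorded | No |
| ECMO | Not recorded | No |

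None of the four is met, yet the code is respiratory failure.

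**Step 3. The pattern of codes in Appendix D (14 rows).**

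- Respiratory failure with the 48-hour extubation rule: rows 4, 5, 7, 8, 9, 12 and 13 (7 rows).
- Respiratory failure with no impact on extubation: rows 6 and 10 (2 rows).
- No impact in either column: rows 1, 2, 3, 11 and 14 (5 rows).

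Row 10 therefore carries the same pair of codes as high-flow cannula, which already has its own row. Low flow handled as high flow would fit this, though the documents do not say so.

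**Step 4. The link to the endpoint.** The endpoint is status at Visit 11 (Day 28 ± 3 days). The footnote to SAP 8.3.2 says that being free of intubation does not need a following period of more than 48 hours without reintubation or noninvasive ventilation. Even a recent extubation to low-flow oxygen can therefore satisfy the endpoint at Visit 11. Row 10 gives that kind of record the opposite code.

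**Step 5. Size for one miscounted participant.** The shift in the arm's crude response rate is 100/n points. Set against the planned difference of 77 − 50 = 27 points, the recorded difference is 27 minus the shift if the participant is in the brexanolone arm, and 27 plus the shift if in the placebo arm.

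| n per arm | Shift (points) | Brexanolone arm | Placebo arm |
|---|---|---|---|
| 50 (planned) | 2 | 25 | 29 |
| 25 (assumed) | 4 | 23 | 31 |
| 10 (assumed) | 10 | 17 | 37 |

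The two smaller sizes are assumptions, because the number analysed is not stated. If no such participant is otherwise failure-free at Visit 11, the shift is zero.

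**The case against.** The mismatch in the text is hard to dispute. The objections concern how far it reaches.

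- **Timing.** Every participant is ventilated before randomization, so Appendix D cannot mean that a support was ever used; it must be applied with dates. Row 10 matters only if it governs status at Visit 11. Protocol 11.1.7 also collects extubation dates and the need for high-flow oxygen or noninvasive ventilation, and those fields may settle the matter. This stands. It makes the effect conditional, but it does not reconcile the two rules.
- **Hypothetical size.** A shift of 1/n follows from any single binary misclassification, and the 27-point difference belongs to a design of about 100 participants. This also stands. The figures show a scale and do not estimate bias in this trial.
- **Ambiguous record.** NC is in neither abbreviation list, L/min is inferred, and the leading None suggests an answer to a form field that is not shown. Parts of the SAP's endpoint section are redacted. Nasal cannula is still the natural reading, and the definition in 8.3.1.1 is visible and unqualified. The ambiguity is a good reason for a blinded query.
- **Weak support.** Protocol 11.1.7 gives only the high-flow threshold and does not define the endpoint. The match with row 6 proves little, since no impact on extubation would also be a natural code for low-flow oxygen. Both points are fair, but the contradiction rests on SAP 8.3.1.1 and Appendix D alone.
- **Safeguard.** SAP section 2 already requires changes after lock to be documented and discussed in the study report. This softens the worry about a late correction but does not remove it.

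**Conclusion.** The concern holds. Appendix D row 10 assigns respiratory failure to a state that meets none of the four criteria in SAP 8.3.1.1, and no visible text explains the exception. Because 8.3.1.1 and 8.3.2 both refer to this table, the written derivation of the primary endpoint is wrong as it stands.

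The conclusion rests on reading 4L NC as 4 L/min by nasal cannula. The size is conditional on a participant whose Visit 11 status is set by this record and who is otherwise alive, analysed and failure-free. Neither an effect on the result nor its direction has been shown. The contradiction is certain and its consequence is not; with so small a remedy, this should be fixed before lock.

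**What to change.** Before database lock and unblinding, recode row 10 in the respiratory-failure column to the no-impact code used in rows 1, 2, 3, 11 and 14. If a blinded query on the record shows that one of the four qualifying supports was in use, classify the participant on that support and document the reason.

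Two clarifying sentences would help, though the correction does not depend on them. One would say that the respiratory-failure column applies to support in use at Visit 11, using the procedure dates and the items in Protocol 11.1.7 on required support. The other would say that mechanical ventilation counts whether given by endotracheal tube or tracheostomy, in line with row 9, which already codes ventilation as failure without naming the airway.

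The cost is one table cell, one or two sentences, and at most a blinded query on the record or records with this term. No extra participants or assessments are needed.
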